9.2 Discussion of Study Design

This is an open-label study to conduct a preliminary assessment of safety and activity of eribulin mesylate in pediatric subjects with relapsed/refractory RMS, NRSTS, or EWS. The secondary objective of PFS is an appropriate surrogate endpoint for studies in STS as there are significant correlations between PFS and OS ($R=0.61$) and between objective response rate (ORR) and OS ($R=0.51$) (Zer, et al., 2016).

9.3 Selection of Study Population

The subject population for this study comprises pediatric subjects aged ≥ 12 months to < 18 years at the time of informed consent, with a histologically confirmed diagnosis of RMS, NRSTS, or EWS, that is considered to be relapsed or refractory (ie, subjects have failed front-line therapy).

Approximately 45 subjects will be enrolled. Subjects who do not meet all of the inclusion criteria or who meet any of the exclusion criteria will not be eligible to receive study drug.

9.3.1 Inclusion Criteria

Subjects must meet all of the following criteria to be included in this study:

1. Age: ≥ 12 months to < 18 years old at the time of informed consent.
2. Diagnosis: Histologically confirmed RMS, NRSTS (Grade 2 or 3) or EWS which is relapsed or refractory (failed front line therapy).
3. The presence of measurable disease meeting the following criteria:
 - At least 1 lesion of ≥ 1.0 cm in the longest diameter for a non-lymph node or ≥ 1.5 cm in the short-axis diameter for a lymph node that is serially measurable according to RECIST 1.1 using CT/MRI.
 - Lesions that have had radiotherapy must show subsequent radiographic evidence of increase in size by at least 20% to be deemed a target lesion.
4. Therapeutic options: Subject's current disease state must be one for which there is no known curative therapy or therapy proven to prolong survival with an acceptable quality of life.
5. Performance level: Performance score $\geq 50\%$. Karnofsky (for subjects > 16 years of age) or Lansky (for subjects ≤ 16 years of age). Subjects who are unable to walk because of paralysis and/or previous surgeries, but who are in a wheelchair, will be considered ambulatory for the purpose of assessing performance score.
6. Subjects must have fully recovered from the acute toxic effects of all prior anticancer therapy and must meet the following minimum duration from prior anticancer directed

therapy prior to study drug administration. If, after the required time frame, the numerical eligibility criteria are met, eg, blood count criteria, the subject is considered to have recovered adequately:

- Cytotoxic chemotherapy or other chemotherapy known to be myelosuppressive: ≥ 21 days after the last dose of cytotoxic or myelosuppressive chemotherapy (42 days if prior nitrosourea).
 - Anticancer agents not known to be myelosuppressive (eg, not associated with reduced platelet or absolute neutrophil count [ANC] counts): ≥ 7 days after the last dose of agent.
 - Monoclonal antibodies: 3 half-lives must have elapsed from infusion of last dose of antibody (including checkpoint inhibitors), and toxicity related to prior antibody therapy must be recovered to Grade ≤ 1 .
 - Hematopoietic growth factors: ≥ 14 days after the last dose of a long-acting growth factor (eg, Neulasta) or 7 days for a short-acting growth factor. For agents that have known AEs occurring beyond 7 days after administration, this period must be extended beyond the time during which AEs are known to occur. The duration of this interval must be discussed with the sponsor.
 - Interleukins, interferons, and cytokines (other than hematopoietic growth factors): ≥ 21 days after the completion of interleukins, interferons or cytokines (other than hematopoietic growth factors).
 - Stem cell infusions (with or without total body irradiation [TBI]): ≥ 84 days.
 - Allogeneic (non-autologous) bone marrow or stem cell transplant, or any stem cell infusion including donor lymphocyte infusion or boost infusion: ≥ 84 days after infusion and no evidence of graft versus host disease (GVHD).
 - Autologous stem cell infusion including boost infusion: ≥ 42 days.
 - Cellular therapy: ≥ 42 days after the completion of any type of cellular therapy (eg, modified T-cells, natural killer cells, dendritic cells, etc).
 - Radiation therapy (XRT)/External Beam Irradiation including Protons: ≥ 14 days after local XRT, ≥ 150 days after TBI, craniospinal XRT or if radiation to $\geq 50\%$ of the pelvis, ≥ 42 days if other substantial BM radiation.
 - Radiopharmaceutical therapy (eg, radiolabeled antibody, ^{131}I -metaiodobenzylguanidine): ≥ 42 days after systemically administered radiopharmaceutical therapy.
7. Adequate bone marrow function, defined as:
- $\text{ANC} \geq 1.0 \times 10^9/\text{L}$
 - Platelet count $\geq 100 \times 10^9/\text{L}$ (transfusion independent, defined as not receiving platelet transfusions within a 7-day period prior to study drug administration)
 - Hemoglobin at least 8.0 g/dL at Baseline (blood transfusions are allowed during the screening period to correct hemoglobin values less than 8.0 g/dL)

Note: As blood transfusions are permitted to meet the hemoglobin criteria, subjects requiring transfusion must not be known to be refractory to red blood cell or platelet transfusions.

8. Adequate renal function, defined as:

- A serum creatinine based on age/gender as follows, derived from the Schwartz formula for estimating glomerular filtration rate (GFR) (see table below)

Age	Maximum Serum Creatinine (mg/dL)	
	Male	Female
6 months to <1 year	0.5	0.5
1 to <2 years	0.6	0.6
2 to <6 years	0.8	0.8
6 to <10 years	1	1
10 to <13 years	1.2	1.2
13 to <16 years	1.5	1.4
≥16 years	1.7	1.4

The threshold creatinine values in this table were derived from the Schwartz formula for estimating glomerular filtration rate (GFR) (Schwartz and Gauthier. *J Pediatr.* 1985;106:522–6) utilizing child length and stature data published by the Centers for Disease Control and Prevention (CDC).

- Or creatinine clearance or GFR ≥ 50 mL/min/1.73 m² based on a 12 or 24 hour urine creatinine collection.

9. Adequate liver function, defined as:

- Bilirubin (sum of conjugated + unconjugated) $\leq 1.5 \times$ upper limit of normal (ULN) for age
- ALT ≤ 110 U/L. For the purpose of this study, the ULN for ALT is 45 U/L.
- Serum albumin ≥ 2 g/dL

10. Informed consent: All subjects and/or their parents or legally authorized representatives must sign a written informed consent. Assent, when appropriate, will be obtained according to institutional guidelines. Subjects must be willing to comply with all aspects of the protocol.

9.3.2 Exclusion Criteria

Subjects who meet any of the following criteria will be excluded from this study:

1. Pregnancy, breastfeeding, contraception: Females who are breastfeeding or pregnant at Screening or Baseline (as documented by a positive beta-human chorionic [β -hCG] (or human chorionic gonadotropin [hCG] test with a minimum sensitivity of 25 IU/L or equivalent units of β -hCG [or hCG]). A separate baseline assessment is required if a negative screening pregnancy test was obtained more than 72 hours before the first dose of study drug.

- Females of childbearing potential* who:
 - Do not agree to use a highly effective method of contraception for the entire study period and for 6 months after study drug discontinuation, ie:
 - Total abstinence (if it is their preferred and usual lifestyle)
 - An intrauterine device (IUD) or intrauterine system (IUS)
 - A contraceptive implant
 - An oral contraceptive**

OR

- Do not have a vasectomized partner with confirmed azoospermia.

For sites outside of the EU, it is permissible that if a highly effective method of contraception is not appropriate or acceptable to the subject, or the subject has commenced/adjusted/changed oral hormonal contraceptive product/dose within 4 weeks prior to study drug administration, then the subject must agree to use a medically acceptable method of contraception, ie, double barrier methods of contraception such as condoms plus diaphragm or cervical/vault cap with spermicide.

*All post pubertal females will be considered to be of childbearing potential unless they have early menopause (amenorrheic for at least 12 consecutive months, in the appropriate age group, and without other known or suspected cause) or have been sterilized surgically (ie, bilateral tubal ligation, total hysterectomy, or bilateral oophorectomy, all with surgery at least 1 month before dosing).

**Must be on a stable dose of the same oral hormonal contraceptive product for at least 4 weeks before dosing with study drug and for the duration of the study and for 6 months after study drug discontinuation.

- Males who have not had a successful vasectomy (confirmed azoospermia) or if they and their female partners do not meet the criteria above (ie, not of childbearing potential or practicing highly effective contraception throughout the study period or for 3 months after study drug discontinuation). No sperm donation is allowed during the study period or for 3 months after study drug discontinuation.

2. Concomitant medications:

- Corticosteroids: Subjects receiving corticosteroids who have not been on a stable or decreasing dose of corticosteroid for at least 7 days prior to study drug administration (except when indicated for Central Nervous System (CNS) metastases, then subjects must not have received corticosteroids for at least 28 days)
- Anticancer Agents: Subjects who are currently receiving other anticancer agents
- Anti-GVHD agents posttransplant:
 - Subjects who are receiving cyclosporine, tacrolimus or other agents to prevent graft-versus-host disease post bone marrow transplant

- Strong CYP3A4 inducers/inhibitors (See [Section 9.4.6.1.1](#), Drug-Drug Interactions).
3. Received prior therapy with eribulin mesylate (when confirmed)
 4. Any other malignancy that required treatment (except for non-melanoma skin cancer, or histologically confirmed complete excision of carcinoma in situ), within 2 years prior to study drug administration.
 5. Has hypersensitivity to eribulin or any of the excipients.
 6. Has a prior history* of viral hepatitis (B or C) as demonstrated by positive serology (presence of antigens) or have an uncontrolled infection requiring treatment (* Subjects with a known prior history of hepatitis B or C may be eligible pending agreement with the sponsor.
 7. Has >Grade 1 peripheral sensory neuropathy or >Grade 1 peripheral motor neuropathy graded according to the Modified (“Balis”) Pediatric Scale of Peripheral Neuropathies
 8. Has cardiac pathology: Subjects with known congestive heart failure, symptomatic or left ventricular (LV) ejection fraction <50% or shortening fraction <27% and subjects with congenital long QT syndrome, bradyarrhythmias, or QTc >480 msec on at least 2 separate ECGs
 9. Has CNS Disease: Subjects with brain or subdural metastases are not eligible unless the metastases are asymptomatic and do not require treatment or have been adequately treated by local therapy (eg, surgery or radiotherapy) and have discontinued the use of corticosteroids for this indication for at least 4 weeks prior to study drug administration. Confirmation of radiographic stability must be done by comparing the brain scan (CT or MRI) performed during the Screening Period, using the same imaging modality, to a brain scan performed earlier (and following local therapy where applicable). Subjects must be clinically stable. It is not the intention of this protocol to treat subjects with active brain metastases.
Note: CNS imaging is required to confirm eligibility for subjects with a known history of CNS disease
 10. Have had or are planning to have the following invasive procedures:
 - Major surgical procedure or significant traumatic injury within 28 days prior to study drug administration
 - Laparoscopic procedure or open biopsy within 7 days prior to study drug administration.
 - Central line placement or subcutaneous port placement is not considered major surgery but must be placed at least 2 days prior to study drug administration.
 - Core biopsy, including bone marrow biopsy within 2 days prior study drug administration
 - Fine needle aspirate within 3 days prior to study drug administration.
 11. Has any serious concomitant illness that in the opinion of the investigator(s) could affect the subject’s safety or interfere with the study assessments
 12. Subjects with known human immunodeficiency virus (HIV); due to lack of available safety data for eribulin therapy in HIV infected subjects.

9.3.3 Removal of Subjects From Therapy or Assessment

The investigator may discontinue treating a subject with study treatment or withdraw the subject from the study at any time for safety or administrative reasons. The subject may decide to discontinue study treatment or withdraw from the study at any time for any reason. The reason for discontinuation will be documented. If a subject discontinues study treatment, the subject will enter the Follow-Up Period and complete protocol-specified off-treatment visits, procedures, and survival follow-up unless the subject withdraws consent. The investigator should confirm whether a subject will withdraw from study treatment but agree to continue protocol-specified, off-treatment study visits, procedures, and survival follow-up, or whether the subject will withdraw consent. If a subject withdraws consent, the date will be documented in the source documents. A subject removed from the study for any reason other than toxicity or progression may be replaced.

During the Follow-Up Period, subjects who have discontinued study treatment without progression should have disease assessments as per the Schedule of Assessments from the date of the last assessment until disease progression as per RECIST 1.1 is documented, death or another anticancer therapy is initiated.

All subjects will be followed for survival until death, except where a subject withdraws consent or the sponsor chooses to halt survival follow-up after completion of the primary study analysis.

9.4 Treatments

9.4.1 Treatments Administered

Eribulin mesylate will be administered by IV infusion over 2-5 minutes on Days 1 and 8 of each 21-day cycle. Eribulin may be diluted in up to 100 mL 0.9% sodium chloride, and administered as an IV infusion over 15 minutes (maximum infusion duration), where clinically appropriate.

9.4.1.1 Criteria for Dosing Modifications

Dose reduction and interruption will be performed according to the instructions in [Section 9.4.1.1.1](#).

9.4.1.1.1 ERIBULIN MESYLATE

Treatment will not be administered when any of the following values are recorded ([Table 5](#)).

Table 5 Criteria for Administration of Eribulin Mesylate

a): Do not administer Cycle 1 Day 1 treatment where:	
Absolute Neutrophil Count	<1.0 × 10 ⁹ /L or 1,000/mm ³

Platelets	$<100 \times 10^9/L$ or 100,000/mm ³
Non-hematological toxicity	Any > Grade 2 except for inadequately treated nausea and/or vomiting
b): Do not administer any Day 8 treatment where:	
Absolute Neutrophil Count	$<0.75 \times 10^9/L$ or 750/mm ³
Platelets	$<75 \times 10^9/L$ or 75,000/mm ³
Non-hematological toxicity	Any > Grade 2 except for inadequately treated nausea and/or vomiting
c): Do not administer any subsequent Day 1 treatment where:	
Absolute Neutrophil Count	$<1.0 \times 10^9/L$ or 1,000/mm ³
Platelets	$<75 \times 10^9/L$ or 75,000/mm ³
Non-hematological toxicity	Any > Grade 2 except for inadequately treated nausea and/or vomiting

If the dose cannot be administered as planned due to treatment-related toxicity, the dose should be delayed according to the following instructions.

Day 1 of each cycle: If treatment cannot be administered on Day 1, the dosing should be delayed until recovery to above these values in [Table 5](#) or Grade ≤ 2 as appropriate (for Cycle 1 & subsequent cycles). The Day 1 dose will be rescheduled for when the criteria for treatment administration are met. The dose level may have to be reduced following a dose delay in accordance to the instructions for dose reduction ([Table 6](#) and [Table 7](#)).

Day 8 of each cycle: If treatment cannot be administered on Day 8, the dosing should be delayed until recovery to above these values ([Table 5](#)). The Day 8 dosing will be **delayed for a maximum of 7 days** and as follows:

- If recovery occurs on or before Day 15, dosing will be resumed at the next lower dose level ([Table 7](#)) and this will be the new Day 8.
- If hematological or non-hematological toxicity has not resolved to the above values on Day 15, the second administration in the cycle will be omitted. Dosing will be resumed at the next lower dose level ([Table 7](#)) and as scheduled on Day 1 of the next cycle if recovery has occurred to the above values.

Please note, use of hematopoietic growth factors is not permitted in Cycle 1 and is only permitted in subsequent cycles as per institutional guidelines.

The treatment will be permanently reduced to the next lowest dose level ([Table 6](#)) after the occurrence of the following events:

Table 6 Criteria for Reduction of Eribulin Mesylate to the Next Lowest Dose Level

Absolute Neutrophil Count	Grade 4 neutropenia > 7 days Grade 3 or 4 febrile neutropenia and/or infection requiring treatment with antibiotics and/or growth factors
Platelets	Grade 4 thrombocytopenia Grade 3 thrombocytopenia requiring platelet or blood transfusion or both
Non-hematological toxicity	Grade 3 or 4 non-hematological toxicities (attributable to study drug); except Grade 3 hypophosphatemia, hypokalemia, hypocalcemia or hypomagnesemia that respond to supplementation

If hematological toxicities do not recover following a dose reduction to dose level -1 and the use of hematopoietic growth factors, the dose should be reduced to dose level -2. If non-hematological toxicities do not recover following a dose reduction to dose level -1, a second dose reduction to dose level -2 should be made. If either hematologic or non-hematologic toxicities do not recover despite two dose reductions, the subject should be discontinued from treatment. However, if the subject is deemed to have clinical benefit, continuation of treatment may be discussed with the sponsor.

Dose modifications are based on AEs for eribulin mesylate (starting dose determined by COG protocol ADVL1314/Eisai Study E7389-A001-113; 1.4 mg/m²; [Table 7](#)).

Dose level	Eribulin mesylate (mg/m²)
0*	1.4
-1	1.1
-2	0.8

* Dose level 0 refers to the starting dose.

Do not re-escalate dose level after the dose level has been reduced.

Instructions for QTc Prolongation on Electrocardiogram (ECG):

[figure not shown]
Increase the frequency of ECG and electrolyte monitoring in subjects who: develop Grade 2 QTc prolongation, are receiving agents that are known to prolong QTc interval, or have clinically relevant electrolyte abnormalities. Permanently discontinue eribulin mesylate in subjects who develop ≥Grade 3 QTc prolongation, and monitor ECGs and electrolytes frequently until the QTc interval returns to baseline.

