Supportive care will be allowed as per institutional guidelines. Growth factors that support platelet or white blood cell number or function can only be administered in accordance with dose modification guidelines or for culture proven bacteremia or invasive fungal infection. Prophylactic granulocyte colony-stimulating factor should NOT be administered during Cycle 1.

Subjects should not receive any other anticancer therapy (including chemotherapy, radiation therapy, immunotherapy or biologic therapy) or investigational agents while receiving study drug. If these therapies are administered, the subject will be removed from the study.

Assessments

Efficacy Assessments

Tumor response and progression will be evaluated according to RECIST 1.1 criteria. Copies of all scans for tumor assessments will be sent to an imaging core laboratory designated by the sponsor for quality assessment, archiving and potential independent review. Tumor assessment scans will be performed following the guidelines provided by the imaging core laboratory. Decisions concerning treatment discontinuation due to progressive disease will be based on investigator assessment.

Tumor assessments (CT chest, and CT or MRI abdomen, pelvis, and other known or suspected sites or disease) will be performed during screening and then every 6 weeks (within the sixth week) on a fixed schedule from the date of first study drug administration. Magnetic resonance imaging scans may be used instead of CT scans for abdomen and pelvis; however, chest must be assessed using CT. Scans that were performed within the screening window, but before informed consent, may be used if they were acquired consistent with the guidelines provided by the imaging core laboratory. The same method of assessment must be used at all time-points as used at pre-study. Partial and complete responses will be confirmed at least 4 weeks after initial documentation of PR or CR typically on the next consecutive scheduled tumor assessment. After 24 weeks subjects with CR, PR or stable disease (SD) may have imaging decreased to every 9 weeks (within the ninth week).

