9.4.6 Prior and Concomitant Therapy

All prior medications (including over-the-counter medications) administered 30 days before the first dose of study drug and any concomitant therapy administered to the subject during the course of the study (starting at the date of informed consent) until 28 days after the final dose of study drug will be recorded. Additionally, all diagnostic, therapeutic, or surgical procedures relating to malignancy should be recorded. Any medication that is considered necessary for the subject's health and that is not expected to interfere with the evaluation of or interact with eribulin may be continued during the study.

Supportive care will be allowed as per institutional guidelines. Growth factors that support platelet or white blood cell number or function can only be administered in accordance with dose modification guidelines or for culture proven bacteremia or invasive fungal infection. Prophylactic granulocyte colony-stimulating factor should NOT be administered in Cycle 1.

Subjects should not receive any other anticancer therapy (including chemotherapy, radiation therapy, immunotherapy or biologic therapy) or investigational agents while receiving study drug. If these therapies are administered, the subject will be removed from the study. From week 24, the subject may receive radiotherapy for local control and continue to receive drug on study.

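### The protocol contradicts itself on whether growth factors may be used to treat infection in Cycle 1

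*Protocol*

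**What the plan says.** The protocol gives its growth factor rule in two places in the body, and the synopsis repeats both.

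- **Dosing rule.** Protocol 9.4.1.1.1 states that "use of hematopoietic growth factors is not permitted in Cycle 1 and is only permitted in subsequent cycles as per institutional guidelines". The synopsis has the same sentence under Criteria for Dosing Modifications.
- **Concomitant therapy rule.** Protocol 9.4.6 says that growth factors supporting platelets or white cells "can only be administered in accordance with dose modification guidelines or for culture proven bacteremia or invasive fungal infection". It then adds: "Prophylactic granulocyte colony-stimulating factor should NOT be administered in Cycle 1". The synopsis, under Concomitant Drug/Therapy, has the same permission and the matching restriction: "Prophylactic granulocyte colony-stimulating factor should NOT be administered during Cycle 1".

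Table 6 in 9.4.1.1.1 (Table 2 in the synopsis) lists the events that lead to a permanent dose reduction. They include "Grade 3 or 4 febrile neutropenia and/or infection requiring treatment with antibiotics and/or growth factors" and "Grade 4 neutropenia > 7 days". Neither is limited to particular cycles.

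For a Day 8 dose that has been held, 9.4.1.1.1 says: "If recovery occurs on or before Day 15, dosing will be resumed at the next lower dose level". If recovery has not occurred by Day 15, that dose is omitted and treatment resumes at the next lower level in the following cycle.

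**The concern.** An investigator needs to know whether a growth factor may be given to a child who develops a proven serious infection in the first cycle. The protocol answers no in the dosing section and yes in the concomitant therapy section.

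This matters for three reasons. It is a safety instruction in a pediatric trial and should have one meaning. The study runs at approximately 40 sites with approximately 15 subjects per histology, so a few different readings could affect the summaries of hematological toxicity and dose intensity (SAP 5.6.1 and 5.6.2). And SAP 5.2.3 has protocol deviations determined before database lock, but the protocol does not settle whether therapeutic use in Cycle 1 is one.

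**Working it through.** No sample size, power or error rate is involved. The check is a comparison of the texts, followed by a short illustration of the route to dosing.

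**Step 1. Set the rules side by side.**

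| Situation | 9.4.1.1.1 and synopsis dosing text | 9.4.6 and synopsis concomitant therapy text |
|---|---|---|
| Cycle 1, prophylactic G-CSF | Barred | Barred |
| Cycle 1, culture-proven bacteremia or invasive fungal infection | Barred, no exception | Allowed, no cycle limit |
| Later cycles | Institutional guidelines | Dose modification guidelines, or the two named infections |

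**Step 2. Does a cross-reference resolve the Cycle 1 row?** No. Section 9.4.6 joins its two grounds with *or*, so infection is a separate ground that does not depend on the dose modification guidelines, where the blanket bar sits. The sentence barring prophylaxis in Cycle 1 would also be redundant if every use were already barred. No section states an order of precedence.

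**Step 3. Does Table 6 resolve it?** No. Infection requiring growth factors is a reduction trigger with no Cycle 1 exclusion. That fits a protocol in which such use can occur in Cycle 1, but it does not grant permission.

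**Step 4. Does a cross-reference resolve the later-cycle row?** Largely. Section 9.4.6 points to the dose modification guidelines. Section 9.4.1.1 places these in 9.4.1.1.1, which defers to institutional guidelines after Cycle 1. If 9.4.6 imports that clause, the two agree, though its restriction then limits little. If it does not, they differ. This is unclear drafting rather than a strict contradiction.

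**Step 5. Follow the route to dosing.** Growth factor use can affect neutrophil recovery, and so whether a held Day 8 dose meets the Day 15 limit. Inputs are the Table 7 levels: 1.4 mg/m² at the start and 1.1 mg/m² one level down. Take a subject at the starting dose whose Cycle 1 Day 8 dose is held, and assume one step down.

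- Planned Cycle 1 dose: 2 × 1.4 = 2.8 mg/m².
- Recovery by Day 15, dose given late: 1.4 + 1.1 = 2.5 mg/m², and 2.5 / 2.8 = 89%.
- No recovery by Day 15, dose omitted: 1.4 mg/m², and 1.4 / 2.8 = 50%.

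The difference is one dose of 1.1 mg/m² in that cycle. The next cycle starts at 1.1 mg/m² in both cases, provided the criteria for dosing are met. This shows what is at stake for one subject whose recovery by Day 15 turns on growth factor use. It does not estimate the effect of the ambiguity on the trial.

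**The case against.** The best defense is that 9.4.6 is permissive and limiting, not mandatory. It says when growth factors may be given and never requires them. A site that gives none in Cycle 1 breaches neither section, and the prophylaxis sentence may simply be redundant. This stands against one stronger reading: a reader might infer that no site can comply with both sections, and the text does not support that. It does not remove the defect, because a site that relies on the infection permission in Cycle 1 follows 9.4.6 and breaches 9.4.1.1.1.

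A second objection is that the dose consequence is small. This largely stands. A reader might take the Table 7 steps, from 1.4 to 1.1 to 0.8 mg/m², as the size of the problem, but they are not differences between the two readings. After a held Day 8 dose the level falls whether or not recovery comes by Day 15. An infection that meets the Table 6 trigger when treated with antibiotics leads to a reduction with or without a growth factor. The duration of Grade 4 neutropenia could depend on growth factor use, but a subject with such an infection already meets a reduction criterion.

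Third, growth factor use would be recorded and summarized as concomitant medication (Protocol 9.4.6 and 9.7.1.5; SAP 5.2.5), so divergent practice would be visible. That helps in reading the results, but it does not tell a site what it may do.

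**Conclusion.** The contradiction is real, stands in the current text, and appears once in the body and once in the synopsis. It is confined to therapeutic use in Cycle 1 for culture-proven bacteremia or invasive fungal infection. What follows is that sites could treat the same event differently and that the status of such use as a deviation is undefined.

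A reader might go further and conclude that sites will differ, or that later cycles hold a second contradiction. The documents support neither: they show only that different readings are possible, and the later-cycle wording can be reconciled through the cross-reference.

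The effect on dosing, where it occurs, is a late rather than an omitted Day 8 dose, with the same dose level afterwards. This rests on growth factor use changing whether recovery falls by Day 15, which is an assumption. The documents give no rate of qualifying infections, so no overall effect on dose intensity or toxicity can be stated. Any effect on the primary responder count would be indirect at most. The point should be corrected because it is a conflicting safety instruction, not because it threatens the primary analysis.

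**What to change.** Reconcile five places: the synopsis text on dosing modifications, the synopsis text on concomitant therapy, and in the body the growth factor sentence in 9.4.1.1.1, Table 6 (with its synopsis copy, Table 2), and 9.4.6. Replace the competing sentences with one statement that covers prophylactic and therapeutic use separately, for Cycle 1 and for later cycles, and have the other places refer to it. For later cycles it should say how the institutional guidelines, the dose modification guidelines and the infection exception relate. The Table 6 trigger should be worded to agree with it.

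Which rule applies is for the sponsor's clinicians. Once it is chosen, the same statement settles which use counts as a deviation under SAP 5.2.3. The cost is a protocol clarification; no change to sample size, endpoints or analysis is needed.
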